### 3. LIST OF ABBREVIATIONS

AE: Adverse event	AE
Body Mass Index	BMI
British Transplant Society	BTS
Cardiovascular	CVS
Chronic kidney disease	CKD
Diabetes Mellitus	DM
Early graft loss	EGL
End-stage renal disease	ESRD
Health Research Authority	HRA
Hypertension	HTN
Implantable Doppler flow probe	IDP
Kidney Disease Outcomes Quality Initiative	KDOQI
National Health Service	NHS
National Health Service	NHS
National Health Service Blood & Transplant	NHSBT
National Kidney Foundation UK	NKF
NHS Trust R&D Department	R&D
Principal Investigator	PI
Renal replacement therapy	RRT
Research Development & Innovation	RD&I
Research Ethics Committee	REC
Serious Adverse Event	SAE
Serious Adverse Reaction	SAR
Standard Operating Procedure	SOP
UK Renal Registry	UKRR
University Hospitals Plymouth NHS Trust	UHPNT

[figure not shown]
#### 4. STUDY SUMMARY

Study Title	The role of an implantable Doppler vascular monitoring device in kidney transplant patients: a feasibility randomised controlled trial with an embedded qualitative study.
Short title/acronym	Continuous Implantable Doppler probe monitoring in renal transplant (CONDOR Study)
Study Settings	Southwest transplant centre at Derriford Hospital, University Hospitals Plymouth NHS Trust
Study Design	Feasibility randomised controlled trial with an embedded qualitative study
Study Aim	To evaluate the feasibility of an implantable continuous vascular monitoring device in kidney transplant patients and to inform the protocol development of a definitive RCT.
Study Objectives	
Objectives “1-3” will be met within the feasibility randomised controlled trial:
 
 
1. To assess the capability of vascular monitoring device in the early postoperative period of kidney transplant patients.
 
2. To assess the research methods used to compare vascular monitoring device with the standard care and to estimate surgical outcome measures essential to inform the sample size calculation for the definitive planned RCT.
 
3. To assess the availability of research resources, management support, potential barriers and challenges for the definitive planned RCT.
 
 
Objectives “4” will be met within the embedded qualitative study:
 
 
4. To assess the acceptability of vascular monitoring device in clinical practice and to acquire suggestions and innovative ideas of the stakeholders on refining the design of definitive RCT, functioning of the implantable vascular monitoring device, and improving postoperative patient care.
 

Trial Participants	50 kidney transplant patients (25 in the intervention and 25 in the control group)
Inclusion criteria	
 
• Patients who will have deceased or living kidney donor transplants at the Southwest Transplant Center.
 
• Patients aged 18 years or above.
 
• Patients able and willing to comply with the trial requirements.
 

Exclusion criteria	
 
• Patients who will have a kidney transplant with more than two arteries (evident at the time of surgery).
 
• Patients below 18 years of age.
 
• Patients lacking capacity or unwilling to give consent.
 

Embedded qualitative study	Using the phenomenology approach, semi-structured interviews with open-ended questions will be conducted with the stakeholders (clinicians, nurses, and kidney transplant patients) directly involved with the implantable vascular monitoring device (n=12). The interviews will be aimed at exploring the experiences of participants (receiving/delivering the intervention) and suggestions of the stakeholders on participating in the study.
Study duration	24 months
Follow up for assessment of outcomes	
 
• In the immediate period after the kidney transplant in recovery,
 
• At 24, 48, and 72 hours postoperatively in the ward
 
• At the three-monthly postoperative clinic visit.
 

Trial Arms	
a) Intervention group: kidney transplant patients with the vascular monitoring device):
 
The kidney transplant patients will receive the Implantable continuous vascular monitoring device surveillance for the first 72 hours in addition to the standard care clinical observation as part of their postoperative care.
 
b) Control group (kidney transplant patients with standard care clinical observation)):
 
The kidney transplant patients will receive the standard care clinical observation as part of their postoperative care.

The Outcomes that will be measured to achieve objectives (1-4)	
Objective 1: To assess the capability of vascular monitoring device in the early postoperative care of kidney transplant patients.	
 
a. The number of early vascular complications identified (incidence).
 
b. The period between the graft implantation and diagnosis of vascular complication (early or late).
 
c. The number of departmental ultrasound scans requested in the first 24, 48, and 72 hours postoperatively.
 
d. The 03-month kidney graft survival
 

Objective 2: To assess the research methods used to compare vascular monitoring device with the standard care and to estimate surgical outcome measures essential to inform the sample size calculation for the definitive planned RCT.	
 
a. Suitability of eligibility criteria and recruitment process.
 
b. Refusal rates for participation and randomization
 
c. Retention and follow-up rates during the research process
 
d. Assessment of the study methods, procedures, and follow-up schedules (researcher and participants)
 
e. Assessment of the procedures for monitoring variation and fidelity in the delivery of the intervention. A fidelity checklist will evaluate the adherence to the standardised protocol of intervention delivery (i.e. consent of the participants, delivery of the intervention, and conduct of the serial Doppler signal monitoring).
 
f. Assessment of the feasibility, appropriateness and performance of the potential outcome measures for the definitive multi-centre RCT.
 
g. Calculation of the means and standard deviation of the outcome
 

	
measures arising from the differences between the intervention and control arm essential to inform sample size calculation for the definitive planned RCT.

Objective 3: To assess the availability of research resources, management support, potential barriers and challenges for the definitive planned RCT.
	
 
a) Assessment of ease and simplicity of the participant documentation (i.e. participant information sheet, consent form, data collection sheet) through the study
 
b) Availability of equipment and medical staff in the host centre to handle the number of participants and the research procedures
 
c) Technological capacity for communication and adequate software to randomize, record, process, and store research data.
 
d) Availability of management support for the research project and back up plans for any extenuating circumstances.
 
e) Documentation of any technical glitches or postoperative complications related to application of the monitoring device.
 
f) To explore factors that will enable future economic evaluation of the vascular monitoring device in the definitive planned RCT (i.e. testing procedures that can collect information to inform a cost effectiveness analysis).
 


5. Objective 4: To assess the acceptability of vascular monitoring device in clinical practice and get suggestions on the protocol development of the definitive planned RCT
	
Exploring the views of stake holders (clinicians, nurses, and patients) regarding receiving/delivering the intervention, participating in the study, and acquiring their suggestions and innovative ideas to improve the design of definitive future RCT, functioning of the implantable vascular monitoring device, or any aspect of postoperative patient care.

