## 16. CONSENT

A kidney transplant is an urgent surgery as the deceased donor organs are offered by the NHS Blood and Transplant at 12-14 hours' notice. After the offer is accepted by the recipient transplant centre, the patient is called in. There is a waiting period of only 8-10 hours during which the recipient is consented and optimised for the surgery.

After the routine surgical consent, it will be the responsibility of the chief investigator (CI) to inform the patients about the study and invite them to participate. In case he is not present due to any emergency, the responsibility will be delegated to the on-call Transplant Consultant who is a regular part of the patient's clinical care team.

Consent to enter the study will be sought from each participant only after a full explanation of recruitment, randomisation, instructions elaborating on the functioning of the device, and allotment to intervention or control group has been given. The participants will be made aware that if they fall in the intervention group, they will have implantable Doppler probe monitoring in the first 72 hours after the surgery in addition to the standard care clinical observation. An information leaflet will also be offered, and time allowed for consideration that would be about six to eight hours. A duly signed informed consent form will be obtained from patients that agree to participate in the study.

All participants will be made aware that they can withdraw from the study anytime from when they give consent to participate till the first 72 hours after the surgery at which the monitoring device will be removed. This will be done regardless of their allotted group, without giving reasons, and prejudicing their treatment. They will also be informed that they have the option to not participate in the study without any change in their postoperative care. The right of a patient to refuse participation in the study without giving reasons will be respected.

All the potential kidney transplant patients are assessed thoroughly at the Southwest transplant centre before activating them on the transplant waiting list. If there is a requirement for special communication needs (i.e. language barrier), an interpreter will be arranged in advance.

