## **18. TRIAL ARMS**

### **18.1. INTERVENTION GROUP (KIDNEY TRANSPLANT PATIENTS WITH THE IMPLANTABLE CONTINUOUS VASCULAR MONITORING DEVICE)**

The intervention that is intended to be investigated is the implantable continuous vascular monitoring device manufactured by COOK Medical Company. Its principle intended use is continuous monitoring of the graft perfusion (i.e. transplanted kidney) for the first 72 hours postoperatively. The kidney transplant patients in the intervention group will receive implantable continuous vascular monitoring device surveillance for the first 72 hours in addition to the standard care clinical observation as part of their postoperative care.

The continuous audible Doppler signals produced by the monitoring device represent the blood flowing in the renal artery. This is an indicator of graft perfusion. Cessation of audible Doppler signals is the key that may suggest hampered blood flow due to vascular complications. In the intervention group, the monitoring device will be used as an added mechanism to monitor graft perfusion. Theoretically, the vascular complications should be identified early, the patients should undergo prompt surgical correction, and better outcomes with less graft loss should be noted in the intervention group as compared to the control group. This scientific basis of the intervention will be tested in this study.

The audible Doppler signals representing the graft perfusion will be monitored continuously by the transplant surgeon till the wound closure in the theatre. In the recovery, the signals will be monitored continuously by the duty nurse till the time patient is transferred to the ward. After that, it will be monitored intermittently as required by the clinician on call in the ward.

The vascular monitoring device is already in use at our hospital by the plastic and reconstructive surgery department, so we do not anticipate any administrative problems with the use of this device. The host renal ward has already trained the nurses and funds have already been allocated to acquire the monitoring devices for the duration of the study. The removal of the monitoring device is a simple and uncomplicated procedure. It will be undertaken 72 hours postoperatively by the duty nurse looking after the patient.

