### 20.1. PARTICIPANT'S DEMOGRAPHIC CHARACTERISTICS

- a. Age at the time of operation in years and months (not the date of birth), gender, and BMI.
- b. Cause of renal deterioration.
- c. Dialysis modality at the time of transplantation
- d. Time on the kidney transplant waiting list
- e. Source of the donated kidney (living versus deceased donor)
- f. Prior renal transplant
- g. Surgeon undertaking the procedure (coded to maintain anonymity)
- h. Recipient risk factors for transplant surgery (age > 70 years, BMI > 30, cardiovascular disease, smoking, peripheral vascular disease, thromboembolic disease, hypertension (HTN), diabetes mellitus (DM), and urological obstructive symptoms)
- i. Donor risk factors for transplant surgery (Donor age > 60 years, BMI > 30, cardiovascular disease, smoking, peripheral vascular disease, hypertension (HTN), diabetes mellitus (DM), cold ischemia time (CIT), cause of death, HLA mismatch, and the number of vessels on the graft).

**20.2. OUTCOME MEASURES FOR OBJECTIVE 1:** To assess the capability of vascular monitoring device in the early postoperative care of kidney transplant patients.

- a) The number of early vascular complications identified and their management (incidence).
- b) The period between the graft implantation and diagnosis of vascular complication (early or late).
- c) The number of departmental ultrasound scans requested by the clinicians taking care of the patients in the first 24, 48, and 72 hours postoperatively.
- d) The 03-month kidney graft survival (the number of grafts lost due to vascular complications in the first 03 months).

**20.3. OUTCOME MEASURES FOR OBJECTIVE 2:** To assess the research methods used to compare vascular monitoring device with the standard care and to estimate surgical outcome measures essential to inform the sample size calculation for the definitive planned RCT.

- a. Suitability of eligibility criteria and recruitment process.
- b. Refusal rates for participation and randomization
- c. Retention and follow-up rates during the research process

- d. Assessment of the study methods, procedures, and follow-up schedules (researcher and participants)
- e. Assessment of the procedures for monitoring variation and fidelity in the delivery of the intervention. A fidelity checklist will evaluate the adherence to the standardised protocol of intervention delivery (i.e. consent of the participants, delivery of the intervention, and conduct of the serial Doppler signal monitoring).

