### Data Collection (Measures, Time-points and Location)

Measures	Time- Points				
	Immediate Postop	At 24 hours Postop	At 48 hours Postop	At 72 hours Postop	At 03 Months Postop
1. Quantitative Study					
a. The number of early vascular complications identified (incidence).	X	X	X	X	
b. The period between the graft implantation and diagnosis of vascular complication (early or late).	X	X	X	X	
c. The number of departmental ultrasound scans requested in the first 24, 48, and 72 hours postoperatively.	X	X	X	X	
d. The 03-month kidney graft survival					X
2. Qualitative Study					
Exploring the views of stake holders regarding				X	
a. Experience with the intervention				X	
b. participating in the study, and				X	
c. acquiring their suggestions to improve the design of definitive future RCT				X	
Location	Operation theatre recovery	Ward	Ward	Ward	Clinic

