## **25. ANTICIPATED FINDINGS OF THE STUDY**

The feasibility RCT and the embedded qualitative component will be conducted concurrently. The outcomes will be measured with descriptive statistics, qualitative analysis, and summarisation of basic data related to the objectives of the study. The findings of both will be integrated at the time of interpretation of the results.

It is anticipated that the results will describe the feasibility of implantable continuous vascular monitoring device in kidney transplant surgery. This study will fill gaps in the evidence, gather necessary information, and test potential research processes to inform the protocol development of a definitive multi-centre RCT.

To summarize, the results of this feasibility study will elaborate on the possible role of vascular monitoring device to improve patient safety, increase graft survival, advance service quality improvement, increase financial savings, and conserve ultrasound resources. They will also highlight learning points from the experiences of stakeholders, inform local practice, and lead to a definitive multicentre RCT in collaboration with other transplant centres.

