### **35. DATA MANAGEMENT PLAN**

A data management plan for this study was prepared under the University of Plymouth's information governance Policy, the UK General Data Protection Regulation (GDPR-2018), and Good Clinical Practice (GCP). It consisted of a complete plan for data protection, retention, and erasure after 10 years.

During the data collection, patient information in fRCT and embedded qualitative study will be pseudonymised and kept strictly confidential by the CI using a unique anonymised code, ensuring it does not contain any patient identifiers.

In the fRCT, the renal database (Vital Data) will be used for the information extraction and is password protected present only on the Trust intranet. The patient's medical notes will be accessed by the CI who is a member of the staff at UHPNT. The notes will not be removed from the premises of the record room. The quantitative data will be logged in the Microsoft spread sheet. In the embedded qualitative study the interviews will be audio-recorded and transcribed verbatim. The pseudonymised transcripts will be noted in the NVivo software.

After transcription of the data, the restriction of access to the Microsoft spread sheet and NVivo software will be maintained by encryption. All data protection measures will be undertaken to maintain the confidentiality of the participants. The official NHS email address will be used for the transfer of any pseudonymised information if required. Data processing and analysis will be performed in the Microsoft Excel worksheet, IBM SPSS version 25.0, and NVivo software. It will be stored in a password secured drive on the Trust intranet.

If there is a requirement to share data with the University of Plymouth or the higher-level data asset owners, the anonymised data file will be exported to the One Drive account of the CI (data asset steward) under the University of Plymouth license.

Two copies of the duly signed written informed consent will be taken from the eligible participants. One copy will be attached in the patient's medical notes along with the routine consent for the kidney transplant surgery. The other copy will be given to the participant. The CI will scan the consent form and keep an electronic copy along with other research documents in a password secured drive on the Trust intranet.

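### Outcome 1(c) counts ultrasound requests only until the probe comes out at 72 hours, so it cannot tell scans avoided from scans moved across that boundary

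*Protocol*

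**What the plan says.** The scan outcome appears in three places, all with the same limit. The study summary (section 4, Objective 1, item c) gives "The number of departmental ultrasound scans requested in the first 24, 48, and 72 hours postoperatively". Section 20.2(c) specifies who makes the requests: "The number of departmental ultrasound scans requested by the clinicians taking care of the patients in the first 24, 48, and 72 hours postoperatively". The data collection table repeats the item and marks it at the immediate, 24, 48 and 72 hour points, with nothing in the 3-month column. The only Objective 1 measure in that column is "d. The 03-month kidney graft survival".

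The probe comes out at the same time. Section 18.1 says of removal: "It will be undertaken 72 hours postoperatively by the duty nurse looking after the patient". Section 16 agrees, describing withdrawal as possible "till the first 72 hours after the surgery at which the monitoring device will be removed".

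No item under Objective 2 or 3 counts scans after 72 hours. Objective 3(f) only explores what a future economic evaluation would need. The SAP document is a data management plan and does not define this outcome.

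Section 25 nevertheless expects the results to elaborate on a possible role for the device to, among other things, "increase financial savings, and conserve ultrasound resources". Section 22 says that the numerical comparison of the arms is to supply parameter estimates for the definitive trial.

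**The concern.** Scan requests are discretionary (section 10) and clinicians know the allocation (section 19). Section 6.4 says that clinicians request scans readily. An audible signal may lead a clinician to hold a scan back. If that scan is requested after the probe is removed, it disappears from outcome 1(c), while the matching control scan on days 1 to 3 is counted. Equally, loss of signal may prompt a scan on day 2 that would otherwise have been requested on day 5. That scan enters the device-arm count, and its control counterpart does not.

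In either case the 72-hour difference mixes a change in the number of scans with a change in their timing. The first bears on resource use and the second does not. A report that read the 72-hour difference as ultrasound conserved, or carried it into a cost argument for the definitive trial, would rest on a count that cannot support it.

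**Working it through.** The documents state no scan rate, expected reduction or decision rule for this outcome, so there is no figure to reproduce. The check is of the time windows, followed by an illustration with assumed inputs.

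**Windows.** Counting runs from 0 to 72 hours (section 4, section 20.2(c), data collection table). Monitoring runs from 0 to 72 hours (sections 16 and 18.1). Observed scan time after removal is therefore zero, although the patient is seen again at 3 months (section 20).

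**What the count can identify.** Per device-arm patient, relative to control, let:
- a = scans truly avoided
- e = extra scans inside the window that would not otherwise have happened
- p = scans postponed from before to after 72 hours
- b = scans brought forward from after to before 72 hours

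Then:
- 72-hour difference = -a + e - p + b
- difference over a window long enough to contain the moved scans = -a + e
- discrepancy = b - p

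The discrepancy is negative (flattering the device) if postponement dominates and positive if bringing forward dominates. It is zero if neither occurs or they balance. Scans that move within the 72 hours do not matter. Nor does a scan requested before 72 hours and performed later, because requests are what is counted.

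**Illustration, postponement only (b = e = 0).** Assume m control scans per patient in 72 hours, a share r of them missing from the device arm by 72 hours, and a share f of the missing ones requested later. Then 72-hour difference = -m × r, longer-window difference = -m × r × (1 - f), and p = m × r × f.

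With m = 2 and r = 0.2, the 72-hour difference is -0.40 scans per patient (mean ratio 0.80; 0.40 × 25 = 10 fewer scans in 25 patients) whatever f is:

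| f | 72-hour difference | Longer-window difference | Postponed (p) |
|---|---|---|---|
| 0 | -0.40 | -0.40 | 0 |
| 0.5 | -0.40 | -0.20 | 0.20 |
| 1 | -0.40 | 0 | 0.40 |

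Over m = 1 to 3, r = 0.2 to 0.4 and f = 0 to 1, p runs from 0 to 3 × 0.4 × 1 = 1.2 scans per patient, or 0 to 30 in an arm of 25 (section 15).

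**Illustration, both movements.** Take m = 2, r = 0.2 and f = 0.5, so a = 0.20 and p = 0.20. If b = 0.20, the discrepancy is 0.20 - 0.20 = 0. If b = 0.40, the 72-hour difference is -0.20 - 0.20 + 0.40 = 0 while the longer-window difference is -0.20, so a real saving would be hidden.

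**Scale against chance.** With 25 per arm and Poisson counts of equal mean m (an assumption), the 95% half-width for the difference in means is 1.96 × √(2m/25): 0.55 for m = 1, 0.78 for m = 2 and 0.96 for m = 3. Postponement of 0.20 at m = 2 is well inside that. Only near the top of the assumed range (0.80 at m = 2, 1.2 at m = 3) does it match or exceed it.

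**The case against.** The 72-hour window is not arbitrary. Objective 1 concerns the early postoperative period, the device is meant for the first 72 hours (section 18.1), and section 10 places the additional scans of usual care in those same hours. As a description of scan use during monitoring, the count is reasonable. Analysis is descriptive, with no test and no decision rule. Section 25 speaks only of a possible role, in a passage on anticipated findings, and Objective 3(f) leaves economic evaluation to the future. All of this stands, and it limits the weight of the point.

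A reader might go further and infer that the truncation can only favour the device. The documents do not support that. Section 18.1 expects earlier identification of complications, and section 6.3 says a compromised graft on the ward would need confirmatory imaging, including ultrasound. Both can pull scans into the window in the device arm, and loss of signal is itself a listed device risk (section 37.5).

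A reader might also infer that the plan scores postponed scans as savings. It does not: it tabulates counts, and the savings reading arises only from section 25.

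What survives is narrower. Section 10 does not say that scanning stops at 72 hours, grafts are followed to 3 months, and a resource statement needs a count that is insensitive to timing.

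**Conclusion.** The point holds in a limited form. The counting window and the monitoring window coincide, so a difference in outcome 1(c) cannot separate avoided scans from scans moved across 72 hours. The net direction of the discrepancy is not fixed.

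Its size is unknown and may be zero, because the documents give neither a scan rate nor evidence that the device defers scans. The range of 0 to 1.2 postponed scans per patient rests wholly on the assumed m, r and f, and ignores scans brought forward. It would be tempting to quote a spurious saving of 20 to 40%, but that figure merely restates the assumed r with every missing scan taken to recur later.

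The 0-72 hour count itself is sound for what it measures. The gap lies between that count and the resource conclusion anticipated in section 25. This is a cheap improvement to a feasibility trial, not a threat to its main purposes.

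**What to change.** Keep the 0-72 hour count as defined. In section 20.2(c), the study summary and the data collection table, add the number of departmental ultrasound scans requested after 72 hours up to the 3-month visit. Report 0-72 hours, after 72 hours and total by arm, each with mean and SD. The definitive trial can then choose its measure; Objective 2(g) does not name the scan count as the outcome that will size it, so there is no need to replace the 72-hour figures with the total. Base any statement about conserving ultrasound on the total. If later scans are not collected, limit the conclusion to scan use during the monitored 72 hours.

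The cost is a wording change and a few data fields. The patient's medical notes are already to be accessed, and section 35 states that "the renal database (Vital Data) will be used for the information extraction". It does not say that this database holds scan requests, so that should be confirmed first. Hospital discharge is not a scheduled time point, so the 3-month visit is the simpler end of the window. The downside is that later scans include some requested for unrelated reasons, which makes the total noisier than the 72-hour count with 25 patients per arm.
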